**Once MLN9708 or pomalidomide is reduced for any toxicity, the dose may not be re-escalated.**

### 7.9.2 Dexamethasone Dose Modification Guidelines\*

Body System	Symptom	Recommended Action
Gastrointestinal	Dyspepsia, gastric or duodenal ulcer, gastritis Grade 1–2 (requiring medical management)	Treat with H2 blockers, sucralfate, or omeprazole. If symptoms persist despite above measures, decrease dexamethasone dose by 1 dose level.
Gastrointestinal	> Grade 3 (requiring hospitalization or surgery)	Hold dexamethasone until symptoms adequately controlled. Restart and decrease one dose level of current dose along with concurrent therapy with H2 blockers, sucralfate, or omeprazole. If symptoms persist despite above measures, discontinue dexamethasone and do not resume.
Gastrointestinal	Acute pancreatitis	Discontinue dexamethasone and do not resume
Cardiovascular	Edema >Grade 3 (limiting function and unresponsive to therapy or anasarca)	Diuretics as needed, and decrease dexamethasone dose by 1 dose level; if edema persists despite above measures, decrease dose another dose level. Discontinue dexamethasone and do not resume if symptoms persist despite second reduction.
Neurology	Confusion or Mood alteration > Grade 2 (interfering with	Hold dexamethasone until symptoms resolve. Restart with one dose level

	function +/- interfering with activities of daily living)	reduction. If symptoms persist despite above measures, discontinue dexamethasone and do not resume.
Musculoskeletal	Muscle weakness > Grade 2 (symptomatic and interfering with function +/- interfering with activities of daily living)	Decrease dexamethasone dose by one dose level. If weakness persists despite above measures, decrease dose by one dose level. Discontinue dexamethasone and do not resume if symptoms persist.
Metabolic	Hyperglycemia > Grade 3 or higher	Treatment with insulin or oral hypoglycemics as needed. If uncontrolled despite above measures, decrease dose by one dose level until levels are satisfactory.

## 7.10 Criteria for Beginning or Delaying a Subsequent Treatment Cycle

For a new cycle of treatment to begin, the patient must meet the following criteria:

- ANC must be  $\geq 1,000/\text{mm}^3$ .
- Platelet count must be  $\geq 75,000/\text{mm}^3$  or  $>=50,000/\text{mm}^3$  for patients with baseline platelets  $\geq 50,000/\text{mm}^3$  but  $<75,000/\text{mm}^3$ .
- All other nonhematologic toxicity (except for alopecia) must have resolved to  $\leq$  Grade 1 or to the patient's baseline condition

If the patient fails to meet the above-cited criteria for initiation of the next cycle of treatment, dosing should be delayed for 1 week. At the end of that time, the patient should be re-evaluated to determine whether the criteria have been met. If the patient continues to fail to meet the above-cited criteria, delay therapy and continue to re evaluate. The maximum delay before treatment should be discontinued will be 3 weeks or at the discretion of the Principal Investigator.

## 7.11 Concomitant Medications

### 7.11.1 Excluded Concomitant Medications and Procedures

The following medications and procedures are prohibited during the study:

Systemic treatment with any of the following metabolizing enzyme inhibitors is not permitted during this study. A drug/drug interaction (DDI) with a strong inhibitor would increase MLN2238 (metabolite of MLN9708) exposure.

- Strong inhibitors of CYP1A2: fluvoxamine, enoxacin, ciprofloxacin
- Strong inhibitors of CYP3A: clarithromycin, telithromycin, itraconazole, voriconazole, ketoconazole, nefazodone, and posaconazole

Systemic treatment with any of the following metabolizing enzyme inducers should be avoided unless there is no appropriate alternative medication for the patient to use. A DDI with a strong inducer would decrease MLN2238 (metabolite of MLN9708) exposure.

- Strong CYP3A inducers: rifampin, rifapentine, rifabutin, carbamazepine, phenytoin, and phenobarbital

Please refer to a complete listing of prohibited medications, strong CYP3A and CYP1A2 inhibitors that can be found via the following link: <http://medicine.iupui.edu/clinpharm/ddis/main-table/>.

The dietary supplements St John's wort and Ginkgo biloba are not permitted.

The following procedures are prohibited during the study:

- Any antineoplastic treatment with activity against MM except for drugs in this treatment regimen.
- Radiation therapy (the requirement for local radiation therapy generally indicates disease progression).
- Platelet transfusions to help patients meet eligibility criteria are not allowed within 3 days before study drug dosing.
- Adjuvant hormone therapy for breast or prostate cancer.

#### **7.11.2 Permitted/Recommended Concomitant Medications and Procedures**

The following medications and procedures are permitted during the study:

- Antiemetics, including 5-HT3 serotonin receptor antagonists, may be used at the discretion of the investigator and is strongly recommended.

- Loperamide or other antidiarrheal should be used for symptomatic diarrhea at discretion of the investigator. The dose and regimen will be according to institutional guidelines. Intravenous fluids should be given to prevent volume depletion.
- Erythropoietin will be allowed in this study. Their use should follow published guidelines and/or institutional practice.
- Patients should be transfused with red cells and platelets as clinically indicated and according to institutional guidelines.
- Concomitant treatment with bisphosphonates will be permitted, as appropriate.
- Patients who experience worsening neuropathy from baseline may be observed for recovery, and have dose reductions/delays as indicated in the protocol, and any supportive therapy or intervention may be initiated as appropriate at the discretion of the investigator.
- Supportive measures consistent with optimal patient care may be given throughout the study.
- Fluid deficits should be corrected before and throughout treatment.

#### **7.11.3 Required/Recommended Concomitant Therapy**

- Pomalidomide increases the risk of thromboembolism. Anti-coagulation prophylaxis is required after an assessment of each patient's underlying risk factors, unless there is an excess risk of bleeding.
- Antiviral therapy such as acyclovir is recommended for herpes prophylaxis.
- For the Phase I portion of the study, growth factors, granulocyte colony stimulating factor [G-CSF], may be given prophylactically for at least two days on days 21 – 26 during or beyond cycle 2. For the Phase II portion of the study, G-CSF may be given prophylactically for at least two days on days 21-26 during or beyond cycle 1. It will be administered subcutaneously at a dose of 5ug/kg or per institutional standard practice dosing either daily or every other day for a minimum of two doses. If patients experience neutropenia or dosing delays, we would recommend consideration of growth factor in subsequent cycles.
- Allopurinol is recommended for patients with high tumor burden due to the possibility of tumor lysis syndrome.

#### 7.11.4 Pregnancy

It is not known what effects MLN9708 has on human pregnancy or development of the embryo or fetus. Pomalidomide can cause fetal harm when administered during pregnancy. Therefore, female patients participating in this study should avoid becoming pregnant, and male patients should avoid impregnating a female partner. Females of child bearing potential\* and male patients should use effective methods of contraception through defined periods during and after study treatment as specified below.

A female of child bearing potential is any sexually mature female who:

- 1) has not undergone a hysterectomy or bilateral oophorectomy; or
- 2) has not been naturally postmenopausal for at least 24 consecutive months (i.e., has had menses at any time in the preceding 24 consecutive months).

##### 7.11.4.1 Females

Females of reproductive potential must commit either to abstain continuously from heterosexual sexual intercourse or to use two methods of reliable birth control simultaneously (one highly effective form of contraception – tubal ligation, IUD, hormonal (birth control pills, injections, hormonal patches, vaginal rings or implants) or partner's vasectomy and one additional effective contraceptive method – male latex or synthetic condom, diaphragm or cervical cap. Contraception must begin 4 weeks prior to initiating treatment, during therapy, during dose interruptions and continuing for 4 weeks following discontinuation of pomalidomide or 90 days following discontinuation of MLN9708. Reliable contraception is indicated even where there has been a history of infertility, unless due to hysterectomy. Females of reproductive potential should be referred to a qualified provider of contraceptive methods, if needed.

Females of reproductive potential must have 2 negative pregnancy tests before initiating therapy. The first test should be performed within 10-14 days, and the second test within 24 hours prior to prescribing pomalidomide and MLN9708. Once treatment has started and during dose interruptions, pregnancy testing for females of reproductive potential should occur weekly during the first 4 weeks of use, then pregnancy testing should be repeated every 4 weeks in females with regular menstrual cycles. If menstrual cycles are irregular, the pregnancy testing should occur every 2 weeks. Pregnancy testing and counseling should be performed if a patient misses her period or if there is any abnormality in her menstrual bleeding. Treatment with pomalidomide and MLN9708 must be discontinued during this evaluation. All study

participants must be registered into the mandatory POMALYST REMS™ program, and be willing and able to comply with the requirements of the POMALYST REMS™ program.

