**Summary of Patient Eligibility Criteria:**

**Inclusion Criteria**

Each patient must meet all of the following inclusion criteria to be enrolled in the study:

1. Male or female patients 18 years or older.
2. Voluntary written informed consent must be given before performance of any study related procedure not part of standard medical care, with the understanding that consent may be withdrawn by the patient at any time without prejudice to future medical care.
3. Females of childbearing potential (FCBP) must have a negative serum or urine pregnancy test with a sensitivity of at least 25 mIU/mL within 10 – 14 days prior to and again within 24 hours of starting pomalidomide and must either commit to continued abstinence from heterosexual intercourse or begin two acceptable methods

of birth control, one highly effective method and one additional effective method at the same time, at least 28 days before she starts taking pomalidomide through 90 days after the last dose of study drug. FCBP must also agree to ongoing pregnancy testing. Men must agree to use a latex condom during sexual contact with a FCBP even if they have had a vasectomy from the time of signing the informed consent form through 90 days after the last dose of study drug.

4. All patients must be registered in and must comply with all requirements of the POMALYST REMSTM program.
5. Patients must have a diagnosis of relapsed or relapsed and refractory Multiple Myeloma with a minimum of one prior regimen and a maximum of 5 prior regimens.
6. Patients must have had therapy with a proteasome inhibitor and lenalidomide and be refractory to lenalidomide according to the IMWG definition of refractory disease (progressive disease on or within 60 days of stopping lenalidomide).
7. Patients must have measurable disease defined as one of the following:
  - Serum M protein  $\geq 0.5$  g/dL
  - Urine M protein  $\geq 200$  mg/24 hours
  - Serum free light chain  $\geq 10$  mg/dL provided the FLC ratio is abnormal.
8. Eastern Cooperative Oncology Group (ECOG) performance status and/or other performance status 0, 1, or 2.
9. Patients must meet the following clinical laboratory criteria:
  - Absolute neutrophil count (ANC)  $\geq 1,000/\text{mm}^3$

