## 4. STUDY DESIGN

### 4.1 Overview of Study Design

#### 4.1.1 Phase I:

The phase I portion of the study is based on a 3 + 3 dose escalation design, to evaluate toxicities associated with MLN9708 when given in combination with pomalidomide and dexamethasone. Two doses of MLN9708 (dose level -1 and dose level 1: 3mg; dose level 2: 4mg) will be tested in up to three possible dose levels. Based on previous combination trials of MLN9708, the 4mg dose of MLN9708 is expected to be well tolerated. Given that this is the first study to combine MLN9708, with dexamethasone and pomalidomide, patients will initially be treated at a 3mg dose. The maximum tolerated dose (MTD) will be established by evaluating dose limiting toxicity (DLT) during cycle 1. The recommended phase II dose (RP2D) of MLN9708 and pomalidomide will generally be the MTD, but it may be less than the MTD based on a review of available data/cumulative toxicities from phase I. Patients will be treated with oral MLN9708 on days 1, 8, and 15 of each 28 day cycle and with Dexamethasone on days 1, 8, 15 and 22 of each 28 day cycle. Pomalidomide will be given on days 1-21 of each 28 day cycle. The dose of MLN9708 and Pomalidomide administered will depend on the dose level assignment; the dose of dexamethasone will be fixed (Patients >75 years, at the time of trial registration, will receive a Dexamethasone starting dose of 20 mg on the same set schedule).

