## 5. STUDY POPULATION

### 5.1 Inclusion Criteria

Each patient must meet all of the following inclusion criteria to be enrolled in the study:

1. Male or female patients 18 years or older.
2. Voluntary written informed consent must be given before performance of any study related procedure not part of standard medical care, with the understanding that consent may be withdrawn by the patient at any time without prejudice to future medical care.
3. Females of childbearing potential (FCBP) must have a negative serum or urine pregnancy test with a sensitivity of at least 25 mIU/mL within 10 – 14 days prior to and again within 24 hours of starting pomalidomide or MLN9708 and must either commit to continued abstinence from heterosexual intercourse or begin TWO acceptable methods of birth control, one highly effective method and one additional effective method AT THE SAME TIME, at least 28 days before she starts taking pomalidomide or MLN9708 through 90 days after the last dose of study drug. FCBP must also agree to ongoing pregnancy testing. Men must agree to use a latex condom during sexual contact with a FCBP even if they have had a vasectomy from the time of signing the informed consent form through 90 days after the last dose of study drug. All patients must be counseled at a minimum of every 28 days about pregnancy precautions and risks of fetal exposure.
4. All patients enrolled into this trial, must be registered in and must comply with all requirements of the POMALYST REMS™ program.
5. Patients must have a diagnosis of relapsed or relapsed and refractory Multiple Myeloma with a minimum of one prior regimen and a maximum of 5 prior regimens.
6. Patients must have had therapy with a proteasome inhibitor and lenalidomide and be refractory to lenalidomide according to the IMWG definition of refractory disease (progressive disease on or within 60 days of stopping lenalidomide).
7. Patients must have measurable disease defined as one of the following:

- a. Serum M protein  $\geq 0.5$  g/dL
- b. Urine M protein  $\geq 200$  mg/24 hours
- c. Serum free light chain  $\geq 10$  mg/dL provided the FLC ratio is abnormal.

8. Eastern Cooperative Oncology Group (ECOG) performance status 0, 1, or 2.
9. Patients must meet the following clinical laboratory criteria:
  - Absolute neutrophil count (ANC)  $\geq 1,000/\text{mm}^3$

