#### **7.11.4.2 Males**

Pomalidomide is present in the semen of males who take pomalidomide. The effects of MLN9708 are unknown. Therefore, males must always use a latex or synthetic condom during any sexual contact with females of reproductive potential while taking pomalidomide or MLN9708 and for up to 28 days after discontinuing pomalidomide or 90 days after discontinuation of MLN9708, even if they have undergone a successful vasectomy. Male patients taking pomalidomide or MLN9708 must not donate sperm. All study participants must be registered into the mandatory POMALYST REMS™ program, and be willing and able to comply with the requirements of the POMALYST REMS™ program.

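### Section 7.11.4 can end contraception before inclusion criterion 3 does: up to 6 days early on its natural reading, 62 days early if *or* is misread as a choice

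*Combined protocol and SAP*

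**What the plan says.** **Inclusion criterion 3** appears in the Protocol Summary and in Section 5.1. For women, the Summary requires contraception "at least 28 days before she starts taking pomalidomide through 90 days after the last dose of study drug". Section 5.1 has the same end point. For men, Section 5.1 requires condom use "from the time of signing the informed consent form through 90 days after the last dose of study drug".

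**Section 7.11.4 (Pregnancy)** says that women of childbearing potential and male patients "should use effective methods of contraception through defined periods during and after study treatment as specified below". Two subsections follow.

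- Section 7.11.4.1 (Females): "Contraception must begin 4 weeks prior to initiating treatment, during therapy, during dose interruptions and continuing for" and then "4 weeks following discontinuation of pomalidomide or 90 days following discontinuation of MLN9708".
- Section 7.11.4.2 (Males): condoms "for up to 28 days after discontinuing pomalidomide or 90 days after discontinuation of MLN9708".

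**The pregnancy reporting procedures in Section 11** make a pregnancy in a female patient immediately reportable if it occurs on either drug or in the 90 days after her last dose of therapy.

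The combined file holds the protocol twice. The wording on this point is the same in both copies.

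**The concern.** Two operative parts of the protocol set the same safeguard and do not agree. Criterion 3 gives one period, 90 days, counted from the last dose. Section 7.11.4 gives two periods joined by *or*. It does not say which one governs, and it does not refer back to criterion 3. For men the periods are also worded as an upper limit.

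The starting point differs as well. Section 7.11.4 counts from discontinuation, which the protocol does not define. Section 7.11.4.1 itself uses the word for a temporary stop: treatment has to be discontinued while a missed period is evaluated. A site therefore has no fixed date from which to count.

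The safeguard concerns fetal exposure. Section 7.11.4 states that pomalidomide can harm a fetus and that the effects of MLN9708 on pregnancy are not known. A clinician who advised a patient from this section alone could end contraception before the eligibility commitment ends, and while a pregnancy in a female patient would still be immediately reportable.

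**Working it through.** The plan gives no derived figure to reproduce here. The check is day arithmetic on the final cycle, counting from its Day 1.

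**Inputs**

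- Last MLN9708 dose, Day 15: "oral MLN9708 on days 1, 8, and 15 of each 28 day cycle" (Section 4.1.1).
- Last pomalidomide dose, Day 21: "Pomalidomide will be given on days 1-21 of each 28 day cycle" (Section 4.1.1).
- Criterion 3: 90 days from the last dose of study drug. I take study drug to mean MLN9708 or pomalidomide.
- Section 7.11.4: 28 days (4 weeks) from pomalidomide discontinuation and 90 days from MLN9708 discontinuation. I date discontinuation from the last dose unless stated otherwise.

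**End of criterion 3:** max(15, 21) + 90 = Day 111.

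**End of Section 7.11.4:** the pomalidomide period ends on 21 + 28 = Day 49. The MLN9708 period ends on 15 + 90 = Day 105.

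| Reading of 7.11.4 | MLN9708 dated | Pomalidomide dated | 7.11.4 ends | Days short of Day 111 |
|---|---|---|---|---|
| Both periods must be met | Day 15 | Day 21 | max(49, 105) = Day 105 | 6 |
| Both periods must be met | Day 21 | Day 21 | max(49, 111) = Day 111 | 0 |
| *Or* as a choice | Day 15 | Day 21 | min(49, 105) = Day 49 | 62 |

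**Sensitivity to the meaning of study drug.** Criterion 3 does not define the term.

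- MLN9708 only: criterion 3 ends on 15 + 90 = Day 105. The shortfalls become 105 − 105 = 0 and 105 − 49 = 56 days.
- Dexamethasone included (last dose Day 22): criterion 3 ends on 22 + 90 = Day 112. The shortfalls become 112 − 105 = 7 and 112 − 49 = 63 days.

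**Sensitivity to the date of discontinuation.** Suppose both drugs were dated as discontinued at the end of the cycle, Day 28. Then the later period ends on 28 + 90 = Day 118, 7 days beyond criterion 3. The choice reading ends on 28 + 28 = Day 56, 111 − 56 = 55 days short. The protocol does not say to date discontinuation in this way, so this is an assumption only.

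**After the fix:** 21 + 90 = Day 111, with no shortfall.

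**The case against.** The strongest reply has four parts.

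1. **Criterion 3 already binds.** Every patient commits to the 90 days on entry, and nothing in Section 7.11.4 waives that. This stands, and it limits the harm: a patient who keeps to the commitment is protected.
2. **The choice reading is not the natural one.** Every patient takes both drugs, so the section is best read as one period per drug, both to be met. The male sentence points the same way. It uses *or* between the two drugs to mean either of them, and it introduces condom use as something that must always happen. This stands, and it is why 62 days cannot be the main figure. The section still leaves the reader to work it out.
3. **The 6 days leave neither drug's own period unmet.** On Day 105 the 90 days after MLN9708 are complete, and the last pomalidomide dose was 105 − 21 = 84 days earlier. The Schedule of Events also uses 28 days after pomalidomide for pregnancy testing. This is true, but criterion 3 sets 90 days from whichever drug was last, and the two rules still differ.
4. **Counselling may come from elsewhere.** The Schedule of Events lists an education and counselling document, including at end of treatment, and the pomalidomide risk programme is mandatory. That document is not in the public file, so one cannot say that patients are told less than 90 days. What can be said is that the protocol text would allow it.

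**Conclusion.** The inconsistency is real and should be corrected. After a full final cycle, Section 7.11.4 ends up to 6 days before criterion 3 on the more natural reading, and 62 days before it if *or* is misread as a choice. These figures assume last doses on Days 15 and 21, discontinuation dated from the last dose, and study drug meaning either of the two agents. The 6 falls to 0 if MLN9708 discontinuation is dated Day 21 or later. Sample size, stopping rules and analyses are untouched.

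A reader might infer three stronger things, which the documents do not support.

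- **That contraception is expected to stop about two months early.** This needs the less natural reading, and it needs criterion 3 to be overlooked.
- **That the gap could reach 90 days if the two drugs stop far apart.** This is an arithmetic bound under the choice reading. The protocol does not spell out permanent discontinuation of MLN9708 or pomalidomide alone, so it is not an expected case.
- **That the protocol separates discontinuing from holding a dose clearly enough to fix the start of the count.** Section 7.11.4.1 requires contraception during interruptions, but it also uses discontinued for a temporary stop.

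**What to change.** In Sections 7.11.4.1 and 7.11.4.2, in both copies of the protocol, replace the drug-specific periods with a single one: *until 90 days after the patient's last dose of MLN9708 or of pomalidomide, whichever is later*. Delete the up-to wording in the male text. This brings the section into line with criterion 3 and the pregnancy reporting window. It also replaces the undefined discontinuation with a recorded dose date and settles which drugs count.

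The cost is a short text amendment, one sentence in each of two subsections, with the approvals from both drug suppliers and the IRB that Section 12.5 requires for any change. Pregnancy testing stays as it is, and no visits, tests or patients are added.
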